### **STUDY DESIGN:**

This study conducted a cluster randomized trial to evaluate an mHealth intervention promoting appropriate GWG in an integrated healthcare system, with randomization at the clinician level. Consented patients received usual care or usual care plus mHealth intervention per their clinician’s randomization. The patient adaptive intervention provided personalized, automated feedback on GWG and physical activity using 1) a smartphone application, 2) a Wi-Fi scale and activity tracker; 3) weekly educational topics; and 4) step-wise support (added when GWG is >75th percentile of the GWG guidelines). Intervention clinicians received newsletters with motivational interviewing tips to facilitate discussing GWG.

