### **STUDY POPULATION:**

#### a. NUMBER OF SUBJECTS

58 total clinicians

1,335 total patients

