**STUDY PROCEDURES:**

Eligible clinicians were randomized into (2) arms: 1) an intervention arm and 2) a usual care arm. Obstetric clinicians randomized to the intervention arm received quarterly newsletters containing study updates on recruitment and retention efforts plus quarterly intervention newsletters containing tips on how to use motivational interviewing techniques to discuss GWG with their pregnant patients. Obstetric clinicians randomized to the usual care arm received quarterly newsletters containing study updates on recruitment and retention efforts.

Pregnant patients receiving prenatal care from consented clinicians were eligible to participate in the trial. Eligible patients of consented clinicians in both arm were invited to complete a trial survey. Patients in both arms were informed they might be invited to an mHealth program. Within one week of completing the survey, patients receiving care from clinicians in the intervention condition were subsequently invited to join the adaptive mHealth intervention and invited to consent to sharing app, activity, and weight data with the study team.

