The approach to the analyses of trimester-specific GWG (kg/week) paralleled that described above for the total rate of GWG. Linear mixed effects models were used in analyses of the intervention in relation to GWG trajectory, accounting for the within-person correlation among repeated measurements (not necessarily equal numbers per subject) and within-clinician correlation between patients, to obtain valid estimates of treatment effects and associated standard errors. We used latent trajectory class modeling to identify and categorize patients with respect to patterns of GWG during pregnancy. Group-based trajectory analysis, an application of finite mixture modeling, is designed to identify clusters of individuals with similar patterns of change over time. Examination of the intervention in relation to pattern of change category utilized multinomial logistic regression with estimation via GEE to account for nesting within clinician. The approach to the analyses of postpartum weight retention at 6 weeks, change in moderate to vigorous physical activity (12 weeks to 33 weeks; MET hrs/week), overall diet quality at 12 weeks (Healthy Eating Index-2015), and birthweight (all continuous), and proportion of infants with appropriate size for gestational age (binary) paralleled that described for the primary outcomes or rate of GWG and meeting the IOM GWG guidelines. The approach to the analyses of the intervention in relation to 12-month infant growth (BMI Z-score) trajectory paralleled that described for analyses of GWG trajectory.

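### Trajectory class is assigned from a mixture model and then analysed as an observed outcome, so the arm effect on latent class is biased unless the classes separate almost perfectly

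*Combined protocol and SAP*

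**What the plan says.** The DATA ANALYSIS section sets out two steps. First: "We used latent trajectory class modeling to identify and categorize patients with respect to patterns of GWG during pregnancy". The model is named as "Group-based trajectory analysis, an application of finite mixture modeling". Second, the category becomes an outcome: "Examination of the intervention in relation to pattern of change category utilized multinomial logistic regression with estimation via GEE", with GEE chosen "to account for nesting within clinician".

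No other source of uncertainty is named for the second step. The section does not mention posterior class probabilities, a correction for classification error, a model with arm as a predictor of class, or resampling over both steps. It also does not give the assignment rule, the number of classes, any measure of class separation, or which weights enter the model.

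**The concern.** Membership of a mixture-model class is estimated, not observed. If each patient is given one class and that class is then the outcome of a regression, errors in assignment become outcome misclassification. The second step has no means of allowing for it. The odds ratio for arm then describes the assigned category, and it is in general not the odds ratio for the latent pattern the model is meant to identify.

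What is at stake is the reported size of the intervention effect on gain pattern, and an interval that may not cover that effect at its nominal rate.

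**Working it through.** The plan states no figure for this analysis, so there is none to reproduce. The sample size comes from the NUMBER OF SUBJECTS section: "1,335 total patients" and "58 total clinicians". Everything else below is an assumption.

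**Two classes, equal error in both arms.** Assume true shares in one class of p = 0.50 (usual care) and 0.40 (intervention), and a probability *a* of correct assignment that is the same in both arms and both classes. The observed share is q = a·p + (1 − a)(1 − p).

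- True log odds ratio: ln(0.40/0.60) − ln(0.50/0.50) = −0.405 (OR 0.667).
- Usual care stays at q = 0.50 for any *a*.
- Intervention at a = 0.80: q = 0.80 × 0.40 + 0.20 × 0.60 = 0.44. The log odds ratio is ln(0.44/0.56) = −0.241, and −0.241/−0.405 = 59% is kept.

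With 1,335 patients split equally and clustering ignored:

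| Accuracy | q, intervention | OR | Log OR | Kept | SE, uncorrected | Coverage of true OR | SE, corrected |
|---|---|---|---|---|---|---|---|
| 0.95 | 0.41 | 0.695 | −0.364 | 90% | 0.110 | 93% | 0.123 |
| 0.90 | 0.42 | 0.724 | −0.323 | 80% | 0.110 | 88% | 0.139 |
| 0.85 | 0.43 | 0.754 | −0.282 | 70% | 0.110 | 80% | 0.159 |
| 0.80 | 0.44 | 0.786 | −0.241 | 59% | 0.110 | 68% | 0.186 |
| 0.70 | 0.46 | 0.852 | −0.160 | 40% | 0.110 | 39% | 0.279 |

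At 98% accuracy q = 0.98 × 0.40 + 0.02 × 0.60 = 0.404, the log odds ratio is ln(0.404/0.596) = −0.389, and 96% is kept.

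The corrected column inverts the error: p = (q − (1 − a))/(2a − 1). At a = 0.80 this gives (0.44 − 0.20)/0.60 = 0.40, the true share. The ratio of estimate to standard error hardly changes: 0.241/0.110 = 2.19 uncorrected and 0.405/0.186 = 2.18 corrected. In this setting the correction restores the size of the effect and gives an interval of the right width, but it does not add power.

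**Simulation with the mixture model estimated.** There were 200 runs per setting, 58 clinicians with 23 patients each (58 × 23 = 1,334), two linear gain classes, ten weights per patient, modal assignment and clinician-robust standard errors. The true log odds ratio was −0.405.

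| Accuracy (entropy) | Mean log OR, true class known | Mean log OR, assigned class | SD of estimate | Mean robust SE | Coverage |
|---|---|---|---|---|---|
| 0.94 (0.78) | −0.404 | −0.347 | 0.113 | 0.115 | 93% |
| 0.85 (0.52) | −0.383 | −0.262 | 0.103 | 0.113 | 80% |
| 0.78 (0.36) | −0.401 | −0.234 | 0.110 | 0.113 | 70% |

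Coverage with the true class known was 94–96%. The robust standard error is about as large as the actual spread, so the missing coverage comes from the shifted centre. With no true effect, the assigned-class test rejected in 7% of runs (Monte Carlo standard error about 1.5 points).

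**Three classes, equal error by arm.** Take correct assignment of 90%, 80% and 90%, with 10% error to each adjacent class. Shares of 0.30/0.40/0.30 (usual care) become 0.31/0.38/0.31, and 0.40/0.40/0.20 (intervention) become 0.40/0.38/0.22. For class 3 v class 1 the true log odds ratio is ln(0.20/0.40) − ln(0.30/0.30) = −0.693, and the observed one is ln(0.22/0.40) − ln(0.31/0.31) = −0.598. All 12 contrasts worked this way shrank. Over 20,000 random three-class settings about 89% of contrasts shrank, about 9% moved away from the null with the same sign, and about 3% changed sign (the counts overlap). These rates depend on the settings drawn. They show only that attenuation is usual and not guaranteed.

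**Unequal data by arm.** The intervention in STUDY DESIGN includes "a Wi-Fi scale and activity tracker". Under STUDY PROCEDURES, patients of intervention clinicians were "invited to consent to sharing app, activity, and weight data with the study team". If those weights entered the model, intervention patients could have more data and less error. Assume 30 weights per intervention patient and 10 per usual-care patient:

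- True log odds ratio 0 (30% in the faster-gain class in both arms): mean estimate +0.24 with about 47% rejection at the larger noise level (SD 8), and +0.14 with 17% rejection at the smaller (SD 6).
- True −0.539 (30% v 20%), SD 8: mean estimate about 0. With the weights reversed (10 intervention, 30 usual care) it was −0.613, and with 10 in each arm −0.302.

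**The case against.** The section is a short summary. It never says that each patient was given the most likely class, and a correction could have been applied without mention. That is fair, but sorting patients into categories and then using the category as a regression outcome is what the text describes, and the only adjustment it names is for clinicians.

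A stronger objection is that the classes may be a convenient summary of continuous variation. There would then be no true class odds ratio to distort, and the assigned category would itself be the outcome. This stands as a limit on the claim: the bias exists only if the result is read as an effect on latent membership. It does not remove the problem of unequal data, because an assigned category that depends on how often a patient was weighed is not comparable between arms.

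It is also true that the plan compares gain over time without classes, through linear mixed models of trajectory and GEE models of trimester-specific gain. A difference in gain between arms would not go unexamined. Those analyses do not estimate class membership, so they reduce the importance of the point without answering it.

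**Conclusion.** The point holds in a limited form, as a minor one. Followed as written, the two-step rule gives a biased estimate of the arm effect on latent class unless separation is near perfect. With equal error by arm, attenuation is the expected direction. Under the assumed two-class shares the loss is about 10% of the log odds ratio at 95% accuracy and about 41% at 80%. The documents give no class count or separation, so the actual loss could be negligible or large.

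A reader might infer more than the documents support:

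- *The effect is necessarily pulled toward null.* That needs error equal by arm, and even then it is not guaranteed for every contrast with three or more classes.
- *An arm difference in measurement distorted the result.* The documents do not say that scale weights entered the model, so this is only a possibility.
- *The interval is too narrow for its own estimate, or the test of no effect is invalid.* With equal measurement the robust standard error was in line with the spread, and 7% rejection does not clearly show an invalid test.
- *The main conclusions are at risk.* The primary outcomes, appropriate gain by the IOM guideline and rate of gain, do not use the classes.

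**What to change.** Estimate the arm effect on class with a bias-adjusted three-step method (BCH or ML), including the covariates planned for the primary analysis. A BCH-weighted third step can still be fitted by GEE with clinician-robust errors, so the marginal approach of the plan is kept. Fit the classes without arm. A one-step model with arm as a class predictor would also address the error, but it lets arm shape the classes.

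Use weights collected in the same way in both arms, and state which they are. Report the assignment rule, the number of classes and how it was chosen, and average posterior probabilities by class and by arm. The by-arm figures matter because a correction that uses one pooled error matrix does not remove error that differs by arm.

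Obtain the interval by resampling clinicians and repeating all steps. Resampling the uncorrected rule would not re-centre it. Keep the assigned-class regression as a descriptive or sensitivity result.

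The cost is modest programming and wider intervals: in the two-class example, a standard error of 0.186 in place of 0.110 at 80% accuracy. No new data are needed. The documents describe the analysis in the past tense, so this may have to be a reanalysis.

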#### b. INCLUSION AND EXCLUSION CRITERIA

Inclusion Criteria:

- Age 21 years or older
- Pregnant
- Women receiving prenatal care at Kaiser Permanente San Francisco and Oakland and whose obstetric care clinicians consent to participate
- Pregravid BMI 25 to <40 (as determined from a measured pregravid weight in electronic medical record)
- Has access to a smartphone and Wi-Fi
- Provides informed consent to participate

Exclusion Criteria:

- Multiple births
- Planning to move out of the area during the study period
- Inability to speak, read, or understand English
- Placed on bed rest at time of enrollment
- > 15 weeks' gestation at enrollment.

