**DATA ANALYSIS:**

All data analyses were intent-to-treat, including all randomized clinicians and patients. Analysis of treatment arm differences was by original treatment group assignment, regardless of adherence. Log binomial regression was used to estimate the population average mHealth intervention effect on meeting the IOM GWG guide lines with estimation via generalized estimating equations (GEE; marginal model), accounting for the within-clinician correlation among patients to obtain valid estimates of treatment effects and associated standard errors. The probability of appropriate total GWG was modeled as a function of treatment arm and covariates used in the randomization procedure: clinician age, patient race/ethnicity, and patient BMI. In addition, this a priori specified set of model covariates included patient age and parity in the regression models given their strong association with GWG.

Linear regression was used to provide point and interval estimates of the between-arm difference in mean rate of GWG. The approach to estimation of model parameters (GEE) and inclusion of model covariates was as specified above for the analysis of our primary binary outcome. Linear regression with GEE was chosen rather than linear mixed effects regression for estimation of population average intervention effects given freedom from

distribution assumptions on cluster random effects, and to parallel the analyses of our binary outcome.

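### HEI-2015 diet quality is compared by arm at 12 weeks on an unstated clock; on the best-supported reading the value precedes, or follows only limited, app exposure

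*Combined protocol and SAP*

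**What the plan says.** The secondary-outcomes paragraph of the Data Analysis section names several outcomes to be analysed in the same way as the primary ones, that is, by arm with GEE. Three of them carry a time point in weeks:

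- Diet: "overall diet quality at 12 weeks (Healthy Eating Index-2015"), a single value and not a change.
- Activity: "change in moderate to vigorous physical activity (12 weeks to 33 weeks; MET hrs/week"), so 12 weeks is the start value.
- Weight: "postpartum weight retention at 6 weeks", the only one of the three with a stated origin.

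The models include the "covariates used in the randomization procedure: clinician age, patient race/ethnicity, and patient BMI", plus the patient's age and parity. The comparison rule is: "Analysis of treatment arm differences was by original treatment group assignment, regardless of adherence".

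Two other sections fix the order of events. The exclusion criteria rule out patients beyond "15 weeks' gestation at enrollment" and set no lower limit. Study Procedures says: "Within one week of completing the survey, patients receiving care from clinicians in the intervention condition were subsequently invited to join the adaptive mHealth intervention". Intervention clinicians also received newsletters with "tips on how to use motivational interviewing techniques to discuss GWG with their pregnant patients".

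**The concern.** One time point has two roles in one sentence. For activity, 12 weeks is where follow-up starts. For diet, 12 weeks is the outcome itself. If both are gestational weeks, diet is measured while patients are still being enrolled, and for some or all intervention patients before the app has been offered.

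At stake is how the diet result is read. A null result could reflect timing alone. A difference could be a chance difference at the start, which the model cannot separate from an effect because it holds no earlier diet value. Followed as written, the plan would report a baseline or barely exposed contrast under the name of an intervention outcome.

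**Working it through.** The plan gives no figure to reproduce here. The check is timeline arithmetic and a comparison of sections.

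**Inputs**
- Diet at 12 weeks; activity from 12 to 33 weeks (Data Analysis).
- Latest enrolment at week 15 of gestation, no lower limit (Inclusion and Exclusion Criteria).
- App invitation after the survey and within one week of it (Study Procedures).
- Assumed: a 40-week pregnancy, and the survey in the week of enrolment. The documents state neither.

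**Step 1: which clock?** If weeks ran from enrolment at gestational week e, the later activity value would fall at week e + 33. That is within pregnancy only if e + 33 ≤ 40, so e ≤ 7. For e = 8 it is 41, and for e = 15 it is 48. An enrolment clock therefore fails for activity over most of the window, and gestational weeks fit. For diet the inference is weaker: it rests on the same number in the same list, and that list also contains a postpartum time point. The postpartum label is attached only to weight retention.

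**Step 2: where does gestational week 12 fall?** Enrolment is open to week 15, so week 12 lies inside the window. A patient enrolled in weeks 13 to 15 cannot have a study-collected value at literal week 12. Either 12 weeks is a nominal label for a survey or visit window, or those patients have no value. The text does not say which.

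**Step 3: what precedes what?** Let s be the survey week. The app cannot start before s, so time on the app by week 12 is at most max(0, 12 − s).
- s ≥ 12: zero.
- s < 12: at most 12 − s weeks, and less if the patient joined later than the survey week.
- Diet taken from the entry survey itself: zero for every patient, whatever s is.

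The distribution of s is not given, so average exposure cannot be calculated.

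**Step 4: the alternative clock.** Twelve weeks after enrolment, with the app starting 0 to 1 week after the survey, gives 12 − 1 = 11 to 12 − 0 = 12 weeks of possible exposure. On that reading the concern does not arise.

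**Step 5: is there an earlier or later diet value?** The five listed covariates (clinician age, race/ethnicity, BMI, patient age, parity) include none. The available text gives no other diet time point. Part of the document was not available for this review, so a schedule elsewhere cannot be excluded.

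**Step 6: comparison with week 33.** For the latest survey (week 15) and the longest invitation interval (1 week), a patient who joined at invitation would have 33 − (15 + 1) = 17 weeks on the app by week 33. A 33-week diet value, if one was collected, would follow substantial opportunity for exposure across the whole window.

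**The case against.** The strongest reply is that nothing here is an error of analysis. Arms are compared by assignment regardless of adherence, so an early contrast is valid, and leaving out a baseline diet covariate does not by itself bias a randomized comparison: chance imbalance is reflected in the standard error. That stands. The contrast is weak, not biased, and a reader who inferred that it is invalid would go too far.

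The reply also notes that the clock for diet is inferred. That stands too, and it is why the conclusion is conditional. It does not remove the point, since a named outcome needs a defined time point.

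Three stronger readings are tempting, and the documents do not support them:
- **No intervention patient had any exposure by week 12.** This follows only if diet came from the entry survey, which is not stated. Early enrolees could have had some weeks on the app, and clinician newsletters are part of the intervention, so no app exposure is not the same as no intervention.
- **The newsletters make 12-week activity an unclean start value.** No section says they had reached patients by then, and their stated subject is discussing GWG.
- **The loss of power can be quantified.** Any such figure needs the share of patients with no exposure and a design power. The documents give neither.

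**Conclusion.** The point holds as a minor one on a single secondary outcome. The time scale and collection time of HEI-2015 are undefined. On the best-supported reading, the planned 12-week contrast cannot support a conclusion for or against a dietary effect: app exposure is nil for patients surveyed at week 12 or later, nil for all if the value came from the entry survey, and otherwise limited and of unstated length. No numerical size can be put on the consequence, because the enrolment weeks are not reported.

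The conclusion rests on three assumptions: that 12 weeks means gestational weeks for diet as well as activity, that pregnancy is taken as 40 weeks in the clock check, and that no diet schedule exists in text not seen. If the first is wrong and weeks run from enrolment, the concern falls away. A reader might extend the doubt to the trial's main result. That does not follow, since the primary GWG analyses do not use the 12-week diet value.

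**What to change.** 1. State the clock for 12 weeks, and when HEI-2015 was collected relative to the survey in both arms and to the app invitation in the intervention arm. If 12 weeks is a misprint for a later value or a change, correct it.
2. If a later HEI-2015 value exists (for example at 33 weeks), make it the diet outcome in the same GEE linear model. Adjust for the 12-week value only where that was taken before the app invitation; adjusting for a value already influenced by the app could remove part of the effect. Label the analysis post hoc unless it was prespecified.
3. If no later value exists, remove 12-week HEI-2015 from the intervention outcomes and report it by arm as a baseline characteristic. If some values followed app start, report it instead as an early measure, with the share of patients exposed and no efficacy conclusion.

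The cost is a few sentences, one tabulation of survey and app-start weeks, and at most one additional model on data in hand. No new data collection is needed. The downside is that one secondary outcome may be lost or carry a post hoc label.
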